5.4.5 Rationale for Blinding (Nivolumab Versus Placebo)

[figure not shown]
The study will be double-blinded in order to minimize bias arising from differences in thresholds for classification of recurrence between the arms, which could subsequently affect treatment duration between the arms and have an impact on the primary endpoint of RFS. In addition, blinding will reduce bias in reporting, classification, and management of adverse events. Participants with recurrence who discontinue treatment may require knowledge of which treatment arm they were assigned to in order to appropriately select any post-recurrence subsequent therapy (including treatment of participants in the optional open-label nivolumab portion of the trial). Therefore, in the event of recurrence of disease and treatment discontinuation of each participant, the participant's treatment assignment will be unblinded via the Interactive Response Technology (IRT) to inform the appropriate subsequent treatment.

[figure not shown]

[figure not shown]

Protocol Amendment No.: 03 Date: 28-Apr-2022

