- Tumor surveillance assessments: Every 26 weeks ± 14 days during the first, second and third year; every 52 weeks ± 28 days from 36 months to 60 months (all timepoints relative to first dose). Participants who develop a loco-regional recurrence only, must be followed by surveillance imaging until the development of distant metastases. Note: If a participant starts systemic therapy for melanoma recurrence after study drug discontinuation, other than optional open-label nivolumab, or for a new non-melanoma cancer, follow-up scans can be done as per standard of care.

• PK/immunogenicity samples: See Table 9.5-1.

Survival Status Follow-Up (in-person or by telephone)

• Every 12 weeks (± 14 days) following the second follow-up visit, calculated from first dose of study treatment until the OS final analysis.

In the event of disease recurrence

РК,

- Treatment unblinding will occur if knowledge of the treatment assignment is necessary to determine subsequent systemic anti-cancer therapy (including participation in the optional open-label nivolumab treatment). Please refer to Section 7.3.1 (Unblinding: emergency, Accidental, and In the Event of Disease Recurrence) for details regarding unblinding.
- Participants agreeing to optional open-label nivolumab treatment: Follow assessments described in detail in Section 2 (Schedule of Activities).
- Participants opting to not participate in open-label nivolumab treatment: Treat per investigator's choice; continue to follow the Schedule of Activities (Table 2-3).
- Submit biopsy tissue at recurrence and de-identified pathology reports of biopsies confirming recurrence to the central vendor.

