7.2.2 Optional Open-Label Nivolumab Treatment After First Recurrence

In the event of recurrence on blinded study treatment, participants may be eligible to receive open-label nivolumab monotherapy. The open-label nivolumab portion of the trial is comprised of two arms, without stratification or randomization. If participants agree to participate in the open-label nivolumab portion of this trial, the participant's treatment assignment in the randomized portion of the trial will be unblinded. Depending on the resectability of the recurrence (resectable versus not), as determined by the investigator/treating physician, participants will be assigned to either Arm 1 (resectable disease) or Arm 2 (unresectable/metastatic disease). The same participant ID assigned in the randomized, blinded portion of the trial will be carried forward in open-label nivolumab treatment phase.

Participants on Arm 1 and Arm 2 will be treated on a nivolumab regimen (480 mg IV Q4W) for a maximum of 12 and 24 months respectively.

Please see Section 7.1.1 further treatment details, including dosing flexibility in pediatrics.

Participants who have received blinded study treatment, experiencing recurrence, but who do not wish to participate in the open-label nivolumab portion of the trial, can be treated per standard of care by the investigator/treating physician and will continue to be followed per follow-up procedures outlined in the Schedule of Activities (Section 2).

For participants receiving open-label nivolumab monotherapy after recurrence, the information collected by the IRT will be similar to that collected prior to randomization, minus the stratification information.

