7.3.2 Unblinding in the Event of Disease Recurrence

Unblinding participants in the event of disease recurrence is necessary for participants who opt to participate in the optional open-label nivolumab component. Unblinding may be requested for election of subsequent systemic therapy (other than participation in optional open-label nivolumab), if the investigator feels that the selection of subsequent systemic therapy may be influenced by knowledge of the treatment assignment.

At the time of recurrence, if the participant's treatment assignment is required to assign the next-line systemic therapy, an unblinding request should be made by the site investigator/staff to the BMS site monitor or a member of the BMS study trial management team, who will gain approval from the Medical Monitor or designee to proceed with unblinding of the treatment arm. The BMS site monitor or a member of the BMS study trial management team will work with the site to unblind the treatment arm through the IRT.

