7.4.1.3 Additional Dose Discontinuation Criteria/Details

- Any event that leads to delay in dosing lasting > 8 weeks from the previous dose requires discontinuation, with the following exceptions:
 - Dosing delays to allow for prolonged steroid tapers to manage drug-related AEs are allowed.
 - Dosing delays lasting > 8 weeks from the previous dose that occur for non-drug-related reasons (including due to COVID-19) may be allowed if approved by the BMS Medical Monitor or designee.
- Any AE, laboratory abnormality, or intercurrent illness which, in the judgment of the Investigator, presents a substantial clinical risk to the participant with continued nivolumab dosing, may require discontinuation.
- Prior to re-initiating treatment in a participant with a dosing delay lasting > 8 weeks, the BMS Medical Monitor or designee must be consulted. Tumor assessments should continue as per protocol even if dosing is delayed. Periodic study visits to assess safety and laboratory studies should also continue every 6 weeks or more frequently if clinically indicated during such dosing delays.
- Study treatment should be discontinued for disease recurrence (local, regional, or distant). Please refer to Section 7.8.1 for continuation of treatment beyond disease recurrence/progression exceptions.

Refer to the Schedule of Activities (Section 2) for data to be collected at the time of treatment discontinuation and follow-up and for any further evaluations that can be completed.

In the case of pregnancy, the investigator must immediately, within 24 hours of awareness of the pregnancy, notify the BMS Medical Monitor or designee of this event. In most cases, the study treatment will be permanently discontinued in an appropriate manner (eg, dose tapering if necessary, for participant safety). Refer to Section 9.2.5, Pregnancy.

All participants who discontinue study treatment should comply with protocol-specified followup procedures as outlined in Section 2. The only exception to this requirement is when a participant withdraws consent for all study procedures including post-treatment study follow-up or loses the ability to consent freely (ie, is imprisoned or involuntarily incarcerated for the treatment of either a psychiatric or physical illness).

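### Does the broader unblinding sentence in Section 5.4.5, or the unspecified monitor in Section 7.3.2, put the blind at risk after recurrence?

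*Combined protocol and SAP*

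**What the plan says.** Protocol Section 5.4.5 gives the reason for blinding as to "minimize bias arising from differences in thresholds for classification of recurrence between the arms". It then observes that participants who recur and stop treatment may need to know their arm so that later therapy can be chosen, and concludes that "in the event of recurrence of disease and treatment discontinuation of each participant, the participant's treatment assignment will be unblinded" through the IRT, for the purpose of guiding that therapy.

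Three other sections deal with the same moment:

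- Section 5.1.1: "Treatment unblinding will occur if knowledge of the treatment assignment is necessary to determine subsequent systemic anti-cancer therapy", which includes entry to open-label nivolumab. For details it refers to Section 7.3.1.
- Section 7.2.2: for those who agree to open-label nivolumab, "the participant's treatment assignment in the randomized portion of the trial will be unblinded". For those who decline it states no unblinding rule.
- Section 7.3.2: unblinding is necessary for open-label entrants; for others, "Unblinding may be requested for election of subsequent systemic therapy". The site asks if the assignment is required, the Medical Monitor or designee approves, and then "The BMS site monitor or a member of the BMS study trial management team will work with the site to unblind the treatment arm", using the IRT.

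On roles, Section 7.2.1 blinds the sponsor, the investigator and site staff, and provides a separate unblinded site monitor. Sections 7.3.1 and 7.5 name the unblinded monitor explicitly; Section 7.3.2 does not use that qualifier. Section 7.2 leaves the exact IRT procedures to the IRT manual.

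**The concern.** Read literally, Section 5.4.5 is automatic while the other sections depend on need. Confining it to recurrences during treatment does not remove the conflict, because Section 7.4.1.3 stops study treatment for a local, regional or distant recurrence, so an on-treatment recurrence would ordinarily meet both of its conditions.

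The participant who shows the difference has a loco-regional recurrence, is treated by surgery alone and declines open-label nivolumab. Section 5.4.5 would unblind that person without need. Section 5.1.1 then says: "Participants who develop a loco-regional recurrence only, must be followed by surveillance imaging until the development of distant metastases". A later distant-metastasis call, which counts for DMFS, would be made by an investigator who knows the arm, and Section 5.1.1 plans no central read. The stated purpose of the blind, equal thresholds in both arms, applies to that call as well.

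The second worry is the route. If the monitor in Section 7.3.2 is the blinded one, assignments could reach sponsor staff who are meant to stay blinded until database lock.

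**Working it through.** The plan states no figure on this point and no formula applies. The check is to set the rules side by side for each kind of participant, and then ask which results could move.

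**Scope of unblinding after first recurrence**

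| Participant | 5.4.5, read literally | 5.1.1 | 7.2.2 | 7.3.2 |
|---|---|---|---|---|
| Enters open-label nivolumab | Unblinded | Unblinded | Unblinded | Unblinded |
| Declines; next systemic therapy depends on the arm | Unblinded | Unblinded | No rule stated | Unblinded on request, after approval |
| Declines; surgery only, or therapy that does not depend on the arm | Unblinded | Stays blinded | No rule stated | Stays blinded |

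The sections disagree only in the third row. A side question is whether 5.4.5 also covers recurrence after the 12 months are complete; its wording can be read either way, but the answer only alters how many people fall in that row.

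**Which text operates.** The sentence in 5.4.5 follows from a premise that participants may need the information, and it ends with the purpose of guiding later treatment. It describes no trigger, requester or approval, only that the IRT is used. Section 7.3.2 carries the title for this situation and supplies all three. Section 7.3.1 also sends any non-emergency request to the Medical Monitor. No automatic release by the IRT is described anywhere, so the third-row participant would be unblinded only if a site asked without needing to and the request were approved.

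**What could move if a third-row participant were unblinded**

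- *RFS.* The event is the first recurrence (Section 10.3.1.1), dated when first observed (Section 9.1.2.4). This unblinding comes after it, so that participant's RFS time is already fixed.
- *Type I error.* The formal tests are RFS, then OS (Section 10.3.4). OS is death from any cause and needs no assessor judgement. DMFS has no multiplicity adjustment (Section 10.3.1.2). The worst outcome is some bias in an estimate.
- *DMFS.* The call is constrained. Cytology or histology is mandatory for solitary or doubtful lesions and for cutaneous, subcutaneous and nodal ones, and is to be attempted otherwise (Section 9.1.2.1). Site-specific criteria are in Table 9.1.2.2-1. Deaths count as events without judgement. Scans are held centrally and may be read blind later (Section 9.1.1).

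**Size.** A count would need the share of recurrences managed without arm-dependent systemic therapy and the uptake of open-label treatment. The documents give neither. The background relapse rates in Section 3.2 (15% to 20% for Stage IIB and 30% for Stage IIC at 24 months) say how many patients relapse, not how many would be unblinded without need, so no number is offered.

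**Route.** Section 7.3 restricts access to codes subject to exceptions set out below it, and 7.3.2 can be read as one of them. It names the roles and the approver. What it leaves open is whether the helper is unblinded and who sees the IRT result, both matters that an IRT manual would normally settle. The Appendix 10 entry for 7.3.2 describes the added team member as helping the site with instructions, which does not require seeing the arm.

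**The case for a change.** The best case for a change is that the conflict is on the face of the text, no sentence gives 7.3.2 precedence, and 5.1.1 refers the reader to 7.3.1, which has recurrence in its title but not the recurrence procedure. Loco-regional relapse is not rare: Section 5.4.1 gives local or in-transit disease as 47% of initial relapses after Stage IIB. Beyond 100 days after blinded treatment, only treatment-related new events are reported (Section 9.2.1), so the investigator's causality call decides what is recorded and is open to bias once the arm is known. On the route, Appendix 10 says the unblinded monitor was named in 7.3.1 to avoid unblinding blinded staff by accident, and 7.3.2 lacks the same word. The remedy would be a few words.

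What stands is that 5.4.5 is worded too broadly, the cross-reference in 5.1.1 is a slip, and the status of the helper in 7.3.2 is unstated.

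The rest carries less weight. A reader who stops at 7.3.1 is still sent to the Medical Monitor, who applies the need-based rule. The 47% describes where relapses occur, not how many are managed without systemic therapy or open-label entry. The causality point matters only for a participant who was in fact unblinded without need. Narrowing the route in 7.3.2 would not seal the sponsor's blind in any case. Under Section 6.1.2 a nivolumab participant must have completed one year and recurred more than six months after the last dose, so an early open-label entrant is recognisable as placebo whichever monitor assists. Restricting support to unblinded staff could also slow requests that guide therapy, and timeliness was the stated reason for adding team members.

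**Conclusion.** No change to the plan follows. The scope conflict is a clerical slip in a rationale paragraph, and the procedure that sites carry out already limits unblinding to cases of need. The silence in 7.3.2 is operational detail that the IRT manual and ordinary role separation would be expected to fill; no leak is shown.

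The effect on RFS and on type I error is nil. The effect on DMFS and on late causality calls is limited to participants unblinded without need; their number cannot be derived and is plausibly very small.

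This rests on three assumptions: sites follow 7.3.2 for unblinding at recurrence; the Medical Monitor approves only requests where the arm is needed; and the IRT does not release the result to blinded staff. If the IRT manual showed automatic release at recurrence, or release to the blinded monitor, the point would need to be reopened.

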5.5 Justification for Dose

5.5.1 Rationale for 480 mg Flat Dose Every 4 Weeks

A nivolumab dose of 480 mg given every 4 weeks (Q4W) was selected for this study based on available PK, safety, and efficacy data.

[figure not shown]
Nivolumab PK has been extensively studied in multiple tumor types, including melanoma, NSCLC, RCC, cHL, SCCHN, CRC, and urothelial carcinoma and has been safely administered at doses up to 10 mg/kg Q2W. Nivolumab monotherapy was originally approved as a body-weight based dose of 3 mg/kg Q2W, and was recently updated to 240 mg Q2W or 480 mg Q4W in multiple indications.¹⁰¹ Less frequent 480 mg Q4W dosing regimens can reduce the burden to patients of frequent, lengthy IV treatments and allow combination of nivolumab with other agents using alternative dosing regimens.

The benefit-risk profiles of nivolumab 240 mg Q2W and 480 mg Q4W are predicted to be comparable to 3 mg/kg Q2W. This assessment is based on a comprehensive characterization of nivolumab PK, safety, efficacy, and exposure-response relationships across indications. Population PK (PPK) analyses have shown that the PK of nivolumab is linear with proportional exposures over a dose range of 0.1 to 10 mg/kg; no clinically meaningful differences in PK across ethnicities and tumor types were observed. Using the PPK model, the exposures following administration of several dosing regimens of nivolumab administered as a flat dose were simulated, including 240 mg Q2W and 480 mg Q4W. The simulated average serum concentration at steady state [Cavgss] following administration of nivolumab 240 mg Q2W and nivolumab 3 mg/kg Q2W administered to participants over a wide body weight range (34-180 kg) across tumor types.

Extensive exposure-response (E-R) analyses of multiple PK measures (maximum serum concentration at Day 1[Cmax1], average serum concentration at Day 28 [Cavg28], and trough serum concentration at Day 28 [Cmin28]) and efficacy and safety endpoints indicated that the efficacy of the flat-dose 480 mg IV regimen are similar to that of 3 mg/kg Q2W IV regimen. In E-R efficacy analyses for OS and ORR conducted in melanoma, RCC, and NSCLC using Cavg28 as the exposure measure, probabilities of achieving a response and survival probabilities at 1 year and 2 years for IV 480 mg Q4W were similar to that of IV 3 mg/kg Q2W. In E-R safety analyses, it was demonstrated that the exposure margins for safety are maintained following nivolumab 480 mg Q4W, and the predicted risks of discontinuations due to AEs or death, AE Grade 3+, and immune-mediated AEs (IMAEs) Grade 2+ are similar following nivolumab 480 mg Q4W relative to nivolumab 3 mg/kg Q2W across tumor types. In addition, nivolumab exposures with 240 mg Q2W and 480 mg Q4W flat-dose IV regimens across tumor types are maintained well below the corresponding exposures observed with the well-tolerated 10 mg/kg IV nivolumab Q2W dose regimen.

Additional details on nivolumab safety and risk-benefit can be found in the investigator brochure.

5.5.3 Rationale for Nivolumab 30-Minute Infusion Duration

Nivolumab is currently approved using a 30-minute infusion as a monotherapy.⁶⁴

6 STUDY POPULATION

For entry into the study, the following criteria MUST be met.

6.1 Inclusion Criteria

6.1.1 Inclusion Criteria - Blinded Nivolumab or Placebo Treatment

1) Signed Written Informed Consent

- a) Participants must have signed and dated an IRB/IEC approved written informed consent form in accordance with regulatory and institutional guidelines. This must be obtained before the performance of any protocol related procedures that are not part of normal participant care.
 - i) For participants unable to give their written consent, in accordance with local regulations, one or both parents, a guardian, or a legally acceptable representative must be informed of the study procedures and must document permission by signing the ICF approved for the study prior to clinical study participation.
 - ii) For minors: Each participant must be informed about the nature of the study to the extent compatible with his or her understanding. Should a participant become capable or reach the age of majority, his or her consent should be obtained as soon as possible. The explicit wish of a participant who is a minor or is unable to provide his or her written consent but who is capable of forming an opinion and assessing information to refuse participation in or to be withdrawn from the clinical study at any time should be considered by the investigator.
 - iii) Minors who are judged to be of an age of reason as determined by local requirements should also give their assent. The assent should be documented based on local requirements. Continued assent should be documented when important new information becomes available that is relevant to the participant's assent.
- b) Participants must be willing and able to comply with scheduled visits, treatment schedule, and laboratory testing.

2) Type of Participant and Target Disease Characteristics

a) Participants must have been diagnosed with Stage IIB/C cutaneous melanoma (AJCC Staging, 8th edition; see Appendix 8) and have histologically confirmed melanoma that is completely surgically resected, with documented negative margins (per local standard) for

disease on resected specimens. All melanomas, except ocular/uveal and mucosal melanoma, regardless of primary site of disease will be allowed. Participants with Stage IIB/C melanoma who present with synchronous or metachronous Stage < 2 melanomas that have been completely resected will be allowed.

NOTE: A copy of the de-identified pathology report(s) confirming Stage IIB or IIC disease and negative margins on the resected specimen must be sent to the Central Laboratory vendor prior to randomization.

- a) Complete resection with documented negative margins (per local standard) and sentinel lymph node assessment for presence/absence of disease, must be performed within 12 weeks prior to randomization. Note: In case of delays exceeding 12 weeks due to unforeseen circumstances, the eligibility should be discussed with the Medical Monitor or designee.
- b) Participants must have a negative sentinel lymph node biopsy. Participants in whom a sentinel lymph node biopsy procedure could not be done or a sentinel lymph node was not detected are not eligible.

NOTE: A copy of the de-identified pathology report confirming sentinel lymph node negativity must be sent to the Central Laboratory vendor prior to randomization.

- c) The pathology report for Stage IIB, IIC, and sentinel lymph node biopsy must be reviewed, and review documented by the investigator.
- d) Participants must have disease-free status documented by a complete physical examination (within 14 days) and imaging studies within 4 weeks (28 days) prior to randomization. Imaging studies must include CT scans of the chest/abdomen/pelvis or CT scan of the chest and MRI scans of the abdomen and pelvis, and all known sites of resected disease (imaging of extremities for resected melanomas located in the extremities is not a requirement and may be conducted per local standard of care). Participants with signs and symptoms consistent with brain metastases should have imaging studies done to rule out the presence of brain metastases.
 - i) Participants with equivocal lymph nodes on imaging (≥ 10 mm and < 15 mm in a short axis) may be eligible if confirmation with histology/cytology is available. If risk of biopsy is too high or biopsy is not feasible, two sequential CT or MRI scans (as listed above) should be available and showing no progressive and measurable (lymph nodes ≥ 15 mm in short axis) disease or PET/CT demonstrating no FDG uptake. The second scan should occur at least 4 weeks after the initial scan. Participants with incidental findings (eg, indeterminate nodules noted on imaging) reported during screening may be eligible if confirmation of disease-free status can be documented by histology/cytology, imaging studies, or in certain situations by discussing with the Medical Monitor or designee. Note: Participants who have had a history of metastatic melanoma and have had their metastatic melanoma resected are not eligible.

- e) The complete set of baseline images must be available before randomization.
- f) Participant has not been previously treated for melanoma beyond complete surgical resection of the melanoma lesion.
- g) Participant has recovered adequately from toxicity and/or complications from surgery prior to study start.

- h) ECOG performance status of 0 or 1 at the time of enrollment (Appendix 6)
- i) Tumor tissue from the primary diagnostic biopsy (minimum of 15 unstained slides, preferably freshly cut, or 1 FFPE block to contain sufficient tissue for at least 15 sections) must be shipped to the central laboratory prior to randomization (see Section 9.8.2 for details). If the required tumor tissue content cannot be provided, the eligibility should be discussed with the Medical Monitor or designee.
- j) Participants must be able and willing to comply with the study visit schedule and study procedures.
- 3) Age and Reproductive Status
 - a) Males and Females, ≥ 12 years of age
 - i) Except: where local regulations and/or institutional policies do not allow for participants < 18 years of age (pediatric population) to participate. For those sites, the eligible participant population is ≥ 18 years of age
 - b) Women of childbearing potential (WOCBP) must have a negative serum or urine pregnancy test (minimum sensitivity 25 IU/L or equivalent units of HCG) within 24 hours prior to the start of study treatment. An extension up to 72 hours prior to the start of study treatment is permissible in situations where results cannot be obtained within the standard 24-hour window.
 - c) Women of childbearing potential (WOCBP) must agree to follow instructions for method(s) of contraception for the duration of treatment with study treatment(s) plus 5 halflives of study treatment plus 30 days (duration of ovulatory cycle) for a total of 5 months after the last dose of study treatment.
- 4) NOTE: As per Protocol Amendment 02, nivolumab IB v19, male study participants will not be required to use contraceptive measures and/or a latex or other synthetic condom during sexual activity with a WOCBP partner. WOCBP who are continuously not heterosexually active are also exempt from contraceptive requirements, and still must undergo pregnancy testing as described in this section.
 - a) Not applicable as per Protocol Amendment 02. Males who are sexually active with WOCBP must agree to follow instructions for method(s) of contraception for a total of 7 months post-treatment completion [ie, 90 days (duration of sperm turnover) plus the time required for study drug to undergo approximately five half-lives]. In addition, male participants must be willing to refrain from sperm donation during this time.
 - b) Not applicable as per Protocol Amendment 02. Azoospermic males are exempt from contraceptive requirements unless the potential exists for fetal toxicity due to study drug being present in seminal fluid, even if the participant has undergone a successful vasectomy or if the partner is pregnant. WOCBP who are continuously not heterosexually active are also exempt from contraceptive requirements, and still must undergo pregnancy testing as described in this section.

Investigators shall counsel WOCBP on the importance of pregnancy prevention and the implications of an unexpected pregnancy and when applicable, the potential of fetal toxicity occurring due to transmission of study drug to a developing fetus. Investigators shall advise on the

use of highly effective methods of contraception (Appendix 4), which have a failure rate of < 1% when used consistently and correctly.

